6.19.7.2. Columbia Suicide Severity Rating Scale

Suicidal ideation, suicidal behavior, and self-injurious behavior without suicidal intent, based on the C-SSRS, will be listed by patient and visit. Only patients that show suicidal ideation/behavior or self-injurious behavior without suicidal intent will be displayed (that is, if a patient's answers are all 'no' for the C-SSRS, then that patient will not be displayed). However, if a patient reported any suicidal ideation/behavior or self-injurious behavior without suicidal intent at any time point then all their ideation and behavior will be displayed, even if not positive.

6.20.3. Annual Report Analyses

Annual report analyses will be stated in a separate document.

6.20.4. Clinical Trial Registry Analyses

Additional analyses will be performed for the purpose of fulfilling the CTR requirements.

Analyses provided for the CTR requirements include the following:

Summary of AEs, provided as a dataset that will be converted to an XML file. Both SAEs and “other” AEs are summarized by treatment group, by MedDRA PT.

- An AE is considered “serious,” whether or not it is a TEAE.
- An AE is considered in the “other” category if it is both a TEAE and is not serious. For each SAE and “other” AE, for each term and treatment group, the following are provided:
 - the number of participants at risk of an event
 - the number of participants who experienced each event term, and
 - the number of events experienced

CCI

- AE reporting is consistent with other document disclosures for example, the CSR, manuscripts, and so forth.

CCI

A large, stylized red logo consisting of the letters 'C', 'C', and 'I' in a serif font, set against a solid black rectangular background.

Appendix 1. Description and Derivation of Efficacy Outcomes Measures and Endpoints

Measure	Description	Variable	Derivation/Comment	Definition of Missing
SLEDAI-2K	The SLEDAI-2K is a global disease activity instrument that focuses on high-impact disease manifestations across 9 organ domains: constitutional, mucocutaneous, musculoskeletal, vascular, cardiorespiratory, central nervous system, immunologic, renal, and hematologic.	SLEDAI-2K Total Score	Calculated by summing the weighted organ manifestation.	Any item scores are missing (not done, not assessed, NA or empty), but the visit occurred. 
 • Baseline data for that item can be carried forward from the last non-missing data during the screening period. • Postbaseline data for that item can be carried forward from the last non-missing data if that data is obtained within the previous 34 days of that visit. After imputation, 
 • If any item is still missing at the baseline visit, it will be imputed as 0. • For Renal domain, if urinary casts, hematuria and pyuria items are still missing for any post-baseline visit, they will be imputed as 0.
		Individual Organ Domain Improvement Defined by SLEDAI-2K	Patients with SLEDAI-2K score >0 within the organ domain at baseline, and able to decrease SLEDAI-2K (from baseline) within each organ domain score, separately.	Missing if any SLEDAI-2K item for that organ domain remains missing after instrument level imputation rules are applied.
		Individual Organ Domain No Worsening Defined by SLEDAI-2K	Among patients with at least one SLEDAI-2K item = 0 (not present) in the organ domain score at baseline, no increment of SLEDAI-2K organ domain score from baseline within each organ domain score, separately.	Missing if any SLEDAI-2K item for that organ domain remains missing after instrument level imputation rules are applied.

[figure not shown]
Measure	Description	Variable	Derivation/Comment	Definition of Missing
		No worsening from baseline in SLEDAI-2K	No increment from baseline of >0 points in SLEDAI-2K	Missing if any SLEDAI-2K item for that organ domain remains missing after instrument level imputation rules are applied.
SLEDAI-4	SLEDAI-4 is an index to measure overall improvement in disease activity (SLEDAI-2K)	SLEDAI-4 Responder	A ≥4-point reduction in SLEDAI-2K score from baseline.	Missing if SLEDAI-2K total score is missing after instrument level imputation rules are applied.
SRI-4	SRI-4 is a composite index to measure overall improvement in disease activity (SLEDAI-2K) while ensuring there is no worsening in other organ systems (BILAG and PGA)	SLE Responder Index 4	
 • A decrease in SLEDAI-2K ≥4 (from baseline) • No new BILAG A and no more than 1 new BILAG B disease activity score / organ domain (both compared with baseline), and • No worsening in PGA (defined as an increase of 0.3 points [10 mm] from baseline) 	After each instrument level imputation rule is applied and there is still at least one missing component, 
 • if the nonmissing components are all 'Y' then SRI-4 is missing. • if any of the nonmissing component is 'N' then the SRI-4 is 'N.'
BILAG-2004	BILAG2004 assesses 97 clinical signs, symptoms and laboratory parameters across 9 organ system domains: constitutional, mucocutaneous, neuropsychiatric, musculoskeletal, cardiorespiratory, gastrointestinal, ophthalmic, renal and hematological	BILAG	A, B, C, D, or E score will be used in analyses for each of the 9 individual organ systems.	Within each organ domain (except renal and hematological), any missing data will be assumed to be 'Not present' if there is at least 1 nonmissing item in that organ. If all items in one organ domain are completely missing but the visit occurred, then the letter score of that organ from the previous visit will be pulled forward, provided data were obtained within 34 days of visit; otherwise missing except when the letter score from the last nonmissing visit is E, then E score will be pulled forward. For the renal and hematological domains,

Measure	Description	Variable	Derivation/Comment	Definition of Missing
				
 • If all item within this domain is 'NA', then items are coded as 'No.' • If any vital/lab item with "Yes" but vital and lab value is missing, then vital/lab values will be pulled forward from scheduled and unscheduled post-baseline visits, provided data were obtained within 34 days of visit; otherwise missing. • If all items in one organ domain are completely missing not 'NA' but the visit occurred, then the letter score of that organ from the previous visit will be pulled forward, provided data were obtained within 34 days of visit; otherwise missing except when the letter score from the last non-missing visit is E, then E score will be pulled forward.
		BILAG improvement	
 • Reduction of all baseline BILAG A to B/C/D and baseline BILAG B to C/D • No BILAG worsening in other organ systems, where worsening is defined as ≥ 1 new BILAG A or ≥ 2 new BILAG B 	For the reduction part, missing if any of 9 domains at baseline or at the visit remains missing after instrument level imputation rules are applied except when the missing is at the baseline (any one or all domains) and the value at the visit is not A or B, then the other non-missing organ domains will be used to determine the response status.

Measure	Description	Variable	Derivation/Comment	Definition of Missing
				
For the no worsening part, Missing if any of 9 domains at baseline or at the visit remains missing after instrument level imputation rules are applied except when the baseline (any one or all domains) is BILAG A and the value at the visit is missing, then the other non-missing organ domains will be used to determine the response status.
 
If both components are missing or one component is missing and the other one is 'Y,' then missing. If at least one component is 'N,' then 'N.'

		No BILAG worsening	
No new BILAG A and no more than 1 new BILAG B disease activity score (both compared with baseline), where worsening is defined as ≥ 1 new BILAG A or ≥ 2 new BILAG B, both compared with the baseline.
 
The baseline BILAG A improved to BILAG B at the visit will not be considered as the new BILAG B.
	
Missing if any of 9 domains at baseline or at the visit remains missing after instrument level imputation rules are applied except when the baseline (any one or all domains) is BILAG A and the value at the visit is missing, then the other nonmissing organ domains will be used to determine the response status.

		Individual Organ Domain Improvement Defined by BILAG	
Among patients with BILAG A or B at baseline and able to reduce the baseline BILAG A to B/C/D and BILAG B to C/D for each organ domain, separately.
	
Missing if baseline or value remains missing after instrument level imputation rules are applied.

Measure	Description	Variable	Derivation/Comment	Definition of Missing
		Individual Organ Domain No Worsening Defined by BILAG	Among patients without BILAG A at baseline, no increment of baseline BILAG B/C/D/E to A and baseline BILAG C/D/E to B for each organ domain, separately.	Missing if baseline or value remains missing after instrument level imputation rules are applied.
PGA	The PGA is the physician’s assessment of the patient’s overall disease activity due to SLE. It is scored using a visual analog scale where 0 mm indicates no disease activity and 100 mm indicates the most severe disease activity possible. There are benchmarks of 0 (0 mm), 1 (33 mm), 2 (67 mm), and 3 (100 mm) on the line corresponding to no, mild, moderate, and severe SLE disease activity, respectively.	PGA score PGA category	Permitted range of values is from 0 to 100 mm. PGA categories are defined as: None (0) = ‘0 mm’, Mild (>0 and <1.5) = ‘>0 to < 50 mm’, Moderate (≥1.5 to ≤2.5) = ‘≥ 50 mm to ≤83mm’, Severe (>2.5) = ‘>83mm’.	If the visit occurred, data can be carried forward if obtained within 34 days of visit; otherwise missing.
		No worsening in PGA	Worsening is defined as an increase of ≥0.3 points (10 mm) from baseline. Therefore, no worsening is defined as any decrease, no change, or <0.3 points (10 mm) increase from baseline.	Missing if baseline or value remains missing after instrument level imputation rules are applied.
		PGA ≤1	PGA ≤33 mm	Missing if value remains missing at the visit after instrument level imputation rules are applied.
BICLA	BICLA is a composite index to measure overall improvement in disease activity (BILAG) while ensuring there is no worsening in other organ systems (SLEDAI and PGA)	BILAG Based Composite Lupus Assessment	
 • BILAG Improvement 
 ○ Reduction of all baseline BILAG A to B/C/D and baseline BILAG B to C/D ○ No BILAG worsening in other organ systems, where worsening is defined as ≥1 new BILAG A or ≥2 New BILAG B • No worsening from baseline in SLEDAI-2K, where worsening is defined as an increase of >0 points from baseline in SLEDAI-2K 	After each instrument level imputation rule is applied and there is at least one component missing, if the non-missing components are all ‘Y’ then BICLA will be missing. If any of the non-missing component is ‘N’ then the BICLA is ‘N.’

Measure	Description	Variable	Derivation/Comment	Definition of Missing
			No worsening from baseline in participants' lupus disease activity, where worsening is defined by an increase ≥ 0.30 points on a 3-point PGA VAS.	

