Visit interval tolerance (days)	—	±3	±3	±3	±3	±3	±3	±3	±3	±3	±3	±3	±3	±3	—	
Fasting visit	X							X						X		
Self-Harm Supplement Form	X	X	X	X	X	X	X	X	X	X	X	X	X	X	X	
Self-Harm Follow-Up Form	X	X	X	X	X	X	X	X	X	X	X	X	X	X	X	Required if triggered by the Self-Harm Supplement Form per instructions.
Laboratory Tests and Sample Collections																
Hematology	X	X	X	X	X	X	X	X		X		X		X	X	
Clinical chemistry	X	X	X	X	X	X	X	X		X		X		X	X	
Lipid panel	X							X						X	X	For the fasting lipid panel, participants should not eat or drink anything but water for 12 hours before the visit. Fasting is not required at an ETV. If a participant attends these visits in a nonfasting state, the sample should still be collected. This will not be considered a protocol violation.
Urinalysis	X			X		X		X		X		X		X	X	
Urine total protein, urine creatinine, and urine protein/urine creatinine ratio (calculation)	X			X		X		X		X		X		X	X	

Treatment period of Study J1P-MC-KFAJ																
For early terminations that occur before the last visit in treatment period, see the activities listed for ETV in this table.																
Visit number	V2	V3	V4	V5	V6	V7	V8	V9	V10	V11	V12	V13	V14	V15	ETV	Comment
Weeks from Randomization	—	1	2	4	6	8	10	12	14	16	18	20	22	24	—	
Study day	1	8	15	29	43	57	71	85	99	113	127	141	155	169	—	
Visit interval tolerance (days)	—	±3	±3	±3	±3	±3	±3	±3	±3	±3	±3	±3	±3	±3	—	
Fasting visit	X							X						X		
Urine pregnancy (local)	X		X	X	X	X	X	X	X	X	X	X	X	X	X	Only for women of childbearing potential (Section 8.2.5.1 and Appendix 10.4) and women with a history of tubal ligation.
HBV DNA								X						X	X	Only for participants who are positive for anti-HBc at screening (Section 8.2.7).

Treatment period of Study J1P-MC-KFAJ																
For early terminations that occur before the last visit in treatment period, see the activities listed for ETV in this table.																
Visit number	V2	V3	V4	V5	V6	V7	V8	V9	V10	V11	V12	V13	V14	V15	ETV	Comment
Weeks from Randomization	—	1	2	4	6	8	10	12	14	16	18	20	22	24	—	
Study day	1	8	15	29	43	57	71	85	99	113	127	141	155	169	—	
Visit interval tolerance (days)	—	±3	±3	±3	±3	±3	±3	±3	±3	±3	±3	±3	±3	±3	—	

Randomization and Dosing																
Randomization	X															
Dosing	X		X	X	X	X	X	X	X	X	X	X	X			No dosing at V3 or V15

Abbreviations: ACR = American College of Rheumatology; [CCI] [REDACTED]
[REDACTED]
[REDACTED] BILAG
= British Isles Lupus Assessment Group; [CCI] [REDACTED] C-SSRS = Columbia–Suicide Severity

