10.7.4. Systemic Lupus Erythematosus Disease Activity Index 2000 (SLEDAI-2K)

The SLEDAI-2K is a validated global disease activity instrument that focuses on disease manifestations across 9 organ systems. It includes 24 clinical and laboratory variables with

manifestations graded by the affected organ system as follows: Central nervous system (CNS) (seizure, psychosis, organic brain syndrome, visual disturbance, cranial nerve disorder, lupus headache, cerebral vascular accident); Vascular (vasculitis); Musculoskeletal (arthritis, myositis); Renal (urinary casts, hematuria, proteinuria, pyuria); Mucocutaneous (rash, alopecia, mucosal ulcers); Cardiovascular and Respiratory (pleurisy, pericarditis); Immunologic (low complement, increased DNA binding); Constitutional (fever); and Hematologic (thrombocytopenia, leukopenia).

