6.14. Primary Endpoint/Estimand Analyses

The primary efficacy endpoint per composite estimand strategy (the primary estimand as described in Section 6.5.1) is

- SLEDAI-4 at Week 24 after accounting for violation of concomitant medication rules: (i) initiating or increasing in dose of corticosteroids, antimalarial, or immunosuppressant, or (ii) using prednisone >10 mg per day (or equivalent) after Week 12

Under the composite estimand strategy, participants will be considered nonresponders at all subsequent visits after the first violation of concomitant medication rules regardless of their discontinuation status.

The primary analysis for treatment comparison of each LY3471851 dose with placebo will be analyzed using a logistic regression model with treatment group, baseline disease activity (SLEDAI-2K <10; SLEDAI-2K ≥10), corticosteroid dose at baseline (<10 mg/day or ≥10 mg/day), and geographic region (North America, Latin America, Europe, Asia, Japan, Rest of World) in the model. The analysis will be based on the mITT population and missing data will be handled using NRI. P-values from the Fisher's exact test will also be reported as a sensitivity analysis, when logistic regression sample size requirements are not met (<5 subjects in any category for any factor).

As supplementary analyses,

- to determine the impact of important protocol deviations, the primary analysis detailed above will also be conducted on the per-protocol population

CCI

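### Three SLEDAI-2K urine items still missing after carry-forward are scored 0 even when last observed positive, so an unobserved resolution can count toward response; the reach is narrow

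*SAP*

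**What the plan says.** The SLEDAI-2K entry in SAP Appendix 1 defines the total as "Calculated by summing the weighted organ manifestation" and does not list the weights. Its missing-data column applies when "Any item scores are missing (not done, not assessed, NA or empty), but the visit occurred". Post-baseline there are two steps.

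1. The item is "carried forward from the last non-missing data if that data is obtained within the previous 34 days of that visit".
2. "For Renal domain, if urinary casts, hematuria and pyuria items are still missing for any post-baseline visit, they will be imputed as 0".

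The fourth renal item, proteinuria, is not in step 2. Protocol 10.7.4 lists the domain as "Renal (urinary casts, hematuria, proteinuria, pyuria".

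For SLEDAI-4 the appendix says "Missing if SLEDAI-2K total score is missing after instrument level imputation rules are applied". SAP 6.14 then closes the chain: "The analysis will be based on the mITT population and missing data will be handled using NRI". So any other item still missing after step 1, proteinuria included, leads to nonresponse. Casts, hematuria and pyuria lead to a score of 0.

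**The concern.** Step 2 has no condition on an earlier positive value. A participant with hematuria when last tested, and no result since, is scored as free of hematuria. The definition of missing covers tests that were not done or not assessed as well as those marked NA, so the rule is not confined to cases where a blank probably means a negative result.

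Two things are at stake. First, the primary endpoint can record an improvement that nobody observed, where the plan's general principle (Protocol 9.4.1, SAP 6.14) would give nonresponse. The same score feeds SRI-4, LLDAS (which requires every renal item to be 0) and the BICLA requirement of no increase in SLEDAI-2K, although each of these has other components that must also be met. Second, the wording names three items joined by *and*. It does not say whether all three must be missing or whether each is handled alone. A participant with one item missing is a nonresponder under the first reading and may be a responder under the second.

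**Working it through.** **Planning figure.** Inputs: 70 per group (Protocol 9.2); response 0.40 on placebo and 0.64 on the most effective dose, two-sided alpha 0.05 (SAP 6.1). The pooled-variance test of two proportions gives power 0.818, which agrees with the stated minimum of 80%. No planning figure is in dispute.

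**When step 2 can act at Week 24.** In the Schedule of Activities (Protocol 1.3), SLEDAI-2K and urinalysis fall on days 113, 141 and 169 (Weeks 16, 20 and 24), each ±3 days.

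- Week 20 to Week 24: 169 − 141 = 28 days, range 22 to 34. An in-window Week 20 value is always carried forward.
- Week 16 to Week 24: 169 − 113 = 56 days, range 50 to 62. A Week 16 value never is.

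So the item must have no value in the 34 days before Week 24, which in practice means missing at both Week 20 and Week 24. Proteinuria must also be available, or the total is missing and NRI applies. That combination is possible, because "Urine total protein, urine creatinine, and urine protein/urine creatinine ratio (calculation" is a separate schedule row from urinalysis, which includes the sediment examination (Protocol 10.2). Exclusion criterion 31 bars active sediment with red-cell casts, which leaves mainly hematuria and pyuria.

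**Crossing the 4-point line.** The documents give no item weight, so let it be w.

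| w | Reduction credited |
|---|---|
| 1 | three items give 3, which is below 4 |
| 2 | two items give 4 |
| 3 | two items give 6 |
| 4 or more | one item is enough |

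Smaller credits matter only on top of a real reduction elsewhere.

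**Share affected.** Assumptions, not in the documents: 5% to 20% have such an item at baseline and it is still positive when last observed; 1% to 5% of those lack it at both Week 20 and Week 24 with proteinuria available. The affected share is a = prevalence × missingness.

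| Prevalence × missingness | a | Per arm of 70 |
|---|---|---|
| 0.05 × 0.01 | 0.0005 | 0.035 |
| 0.10 × 0.03 | 0.003 | 0.21 |
| 0.20 × 0.05 | 0.010 | 0.70 |

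**Equal loss in both arms.** Let p be the true response rate. Under the rule at its worst, every affected true nonresponder is converted: p + a(1 − p). If the affected cases go to NRI instead: p(1 − a). In both cases the difference is 0.24(1 − a).

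| a | Scoring | Placebo | Active | Difference (points) | Power |
|---|---|---|---|---|---|
| 0 | plan | 0.4000 | 0.6400 | 24.0 | 0.818 |
| 0.003 | rule, worst case | 0.4018 | 0.6411 | 23.9 | 0.816 |
| 0.003 | NRI | 0.3988 | 0.6381 | 23.9 | 0.816 |
| 0.01 | rule, worst case | 0.4060 | 0.6436 | 23.8 | 0.811 |
| 0.01 | NRI | 0.3960 | 0.6336 | 23.8 | 0.810 |

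At a = 0.01 the rule wrongly credits at most 70 × 0.01 × 0.60 = 0.42 placebo and 70 × 0.01 × 0.36 = 0.25 active participants, 0.67 in total. NRI wrongly fails 70 × 0.01 × 0.40 = 0.28 and 70 × 0.01 × 0.64 = 0.45, 0.73 in total.

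**All loss in the active arm, true rate 0.40 in both.** Exact binomial enumeration of the pooled test:

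| Case | Active rate | Significant in favour of drug | Two-sided |
|---|---|---|---|
| no loss | 0.400 | 0.0243 | 0.0485 |
| a = 0.01, rule | 0.406 | 0.0287 | 0.0492 |
| a = 0.01, NRI | 0.396 | 0.0216 | 0.0488 |

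The third column is one-directional and should be read against 0.025. The two-sided rate stays below 0.05 in every row.

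**The case against.** The strongest defence has four parts.

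- **Carry-forward already uses the last observed value.** This is true within 34 days, and it removes most cases. It does not remove the residual case, in which an older positive result is overridden by 0.
- **Treating a blank as absent is a habit of this SAP.** In the BILAG-2004 entry, a renal domain marked NA throughout is coded as no, and outside the renal and hematological domains missing items count as not present if at least one item was observed. But the same entry leaves a renal domain missing when it is wholly empty rather than NA, cannot be pulled forward within 34 days and was not last scored E. The SLEDAI-2K rule draws no such distinction, so the convention explains the rule without covering a last positive result.
- **NRI misclassifies about as many people.** On the figures above this stands (0.73 against 0.67). The case for change is that a response should rest on an observed result. It is not a case for greater accuracy or power.
- **The column works item by item, so the all-three reading is strained.** Largely true, but settling it costs two words.

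A reader might infer that the rule biases the trial toward the drug or inflates its error rate. The documents do not support that. Nothing suggests that urine microscopy would be lost more often in one arm, and even with all loss in the active arm at the top of the assumed range the two-sided rate is 0.0492.

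**Conclusion.** The point holds, as a minor one. The SLEDAI-2K rule can turn a last observed positive urine item into a resolved one without a result, and it prevents NRI from acting on the primary endpoint and on the secondary endpoints built on the same score. The documents visible to this review give no reason for it and plan no sensitivity analysis of it.

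The size is probably well under one participant per arm of 70. That rests on assumed prevalence (5% to 20%) and missingness (1% to 5%). The documents supply neither, nor the item weights, so the size cannot be derived from them. It would also be too strong to say that the primary result is at risk or that the change would recover power: power at a 1.0% affected share is 0.811 under the rule and 0.810 after the change.

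**What to change.** Replace the renal sentence in SAP Appendix 1 with:

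> After carry-forward, each of these items, taken separately, is set to 0 only if its last observed value (baseline or later) was 0, or if the laboratory records that microscopy was not done because the same-visit urinalysis was negative; otherwise the item and the SLEDAI-2K total stay missing, with NRI for responder endpoints and a missing value in the MMRM.

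The condition is tied to the last observed value on purpose. Requiring 0 at baseline as well would fail a participant whose item was positive at baseline and later observed as 0. The MMRM is named because the total also feeds the change-from-baseline analysis in SAP Appendix 2, where NRI has no meaning. Use the same derivation for SLEDAI-4, SRI-4, LLDAS and BICLA.

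Report by arm how many participants had an item set to 0 at Week 24 and how many responders depend on it.

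The cost is one sentence, one count table and a small programming change. The downside is that a few participants whose item truly resolved after a last positive result count as nonresponders: at a 1.0% affected share, at most 0.28 on placebo and 0.45 on active per arm of 70.

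### The BILAG no-worsening rules in SAP Appendix 1 score a domain still missing at baseline as unresolvable even when its visit score is C, D or E, and so cancel the SAP's own exception for that case

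*SAP*

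**What the plan says.** SAP Appendix 1 states a BILAG no-worsening rule twice: as its own row, which corresponds to the BILAG component of SRI-4, and as the second part of *BILAG improvement*, which is the BILAG component of BICLA. Worsening means at least one new A or at least two new Bs against baseline.

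- The reduction part and both no-worsening rules open with the same condition. In the reduction part it reads "missing if any of 9 domains at baseline or at the visit remains missing after instrument level imputation rules are applied".
- The reduction part then makes an exception: "except when the missing is at the baseline (any one or all domains) and the value at the visit is not A or B". The other domains decide in that case.
- Both no-worsening rules make a different exception, and only that one: "except when the baseline (any one or all domains) is BILAG A and the value at the visit is missing".
- To combine the two parts: "If both components are missing or one component is missing and the other one is" Y, BILAG improvement is missing. An N in either part gives N.
- SRI-4: "After each instrument level imputation rule is applied and there is still at least one missing component", the result is missing when the rest are Y and N when any is N. BICLA follows the same pattern: if all other components are Y, "then BICLA will be missing".
- SAP 6.11 turns missing binary outcomes into nonresponse under NRI. Sections 6.14 and 6.15 and Appendix 2 apply NRI to SRI-4 and BICLA.

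On filling gaps, where a renal or hematological item is marked present but its value is missing, "then vital/lab values will be pulled forward from scheduled and unscheduled post-baseline visits", within 34 days. For SLEDAI-2K the rule differs: "Baseline data for that item can be carried forward from the last non-missing data during the screening period", and an item still missing at baseline is set to 0. SAP 6.4 defines baseline in general as the latest value on record ahead of dosing, unless otherwise specified.

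**The concern.** A new A or B needs an A or B at the visit. A domain scored C, D or E at the visit cannot be a worsening, whatever its baseline was. The baseline score is not needed to settle the question, yet the no-worsening rules treat its absence as fatal.

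The SAP accepts this reasoning twice. The reduction part ignores a domain that is missing at baseline and not A or B at the visit. The no-worsening exception ignores a domain that was A at baseline and is missing at the visit, because no score there could be a new A or B. A missing baseline with a visit score of C, D or E meets the same test and was left out.

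Baseline does not change, so the consequence runs through all six post-baseline BILAG visits (Weeks 4 to 24). Two of the three secondary efficacy endpoints are involved, with the subgroup analyses of SRI-4 and possibly BICLA in SAP 6.20.1. A participant whose response can be determined from the data would be counted as a failure.

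**Working it through.** **1. The plan's own figure.** Inputs: 70 per arm (Protocol 9.2), 0.40 versus 0.64 (SAP 6.1), two-sided 0.05. With the pooled null standard error:

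- SE0 = √(2 × 0.52 × 0.48 / 70) = 0.0844
- SE1 = √((0.40 × 0.60 + 0.64 × 0.36) / 70) = 0.0820
- power = Φ((0.24 − 1.96 × 0.0844) / 0.0820) = Φ(0.909) = 81.8%

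This reproduces the stated minimum of 80%. It is a SLEDAI-4 figure; the plan gives none for SRI-4 or BICLA.

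**2. One participant traced through the rules.** One domain is missing at baseline after all instrument-level rules and C at the visit. Every other domain is observed and meets both parts. The SLEDAI-2K and PGA criteria are met.

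| Element | Rule that applies | Result |
|---|---|---|
| Reduction part | Exception: baseline missing, visit not A or B | Y |
| No worsening | Only exception needs baseline A with visit missing | missing |
| BILAG improvement | Y with missing | missing |
| BICLA | Other components Y | missing, then nonresponse |
| SRI-4 | Other components Y | missing, then nonresponse |

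The unscored domain cannot be a new A or B, so no-worsening is in fact settled, as Y, by the other domains.

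**3. All patterns.** The rules work domain by domain, so four domains are enough to test them. One is missing at baseline, the other three are A to E at baseline, and each visit score is A to E or missing: 5³ × 6⁴ = 125 × 1,296 = 162,000 patterns, with all non-BILAG components set to Y.

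- Domain-by-domain reading: SRI-4 is Y in 0 of 162,000. BICLA is Y in 0 (147,069 missing, 14,931 N).
- Participant-level reading: suppose a different domain is A at baseline and missing at the visit, and the instruction to use the remaining domains is taken to cover the whole participant. SRI-4 is then Y in 11,544 patterns. BICLA is still Y in 0, because the reduction part has no relief for a missing visit score.
- The reduction exception applies, with no other score missing, in 125 × 3 × 125 = 46,875 patterns. It changes the BICLA result after NRI in 0 of them.

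With the no-worsening exception extended to the same case, 26,244 of those 46,875 give SRI-4 = Y and 11,181 give BICLA = Y within the BICLA subset. The first count can be checked by hand. Of the 25 baseline-visit pairs in a domain, 4 are a new A, 3 a new B and 18 neither, so 3 × (18³ + 3 × 3 × 18²) = 3 × (5,832 + 2,916) = 26,244. These are counts of logical patterns, not patient frequencies.

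**4. Size, illustrative only.** The documents give no rate of unresolved baseline domains. Assume a share m in every arm, and borrow the SLEDAI-4 rates and 70 per arm. Both rates are multiplied by (1 − m), so the difference is 24.0 × (1 − m) points.

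| Assumed m | Difference (points) | Power |
|---|---|---|
| 0 | 24.0 | 81.8% |
| 1% | 23.8 | 81.0% |
| 2% | 23.5 | 80.2% |
| 5% | 22.8 | 77.6% |
| 10% | 21.6 | 73.1% |

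One affected responder is 1/70 = 1.4 points in an arm of 70. For scale, Protocol 4.2 reports that in earlier trials 0.3% to 2.2% of participants with a 4-point SLEDAI reduction failed SRI-4 through BILAG or PGA worsening. On the borrowed rates, one false failure is 1/28 = 3.6% of placebo responders (0.40 × 70 = 28) or 1/44.8 = 2.2% of active responders (0.64 × 70 = 44.8).

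**The case against.** The strongest reply is about reach, and much of it stands.

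- A reader might infer that any participant with a gap in the baseline BILAG becomes a nonresponder. The documents do not support that. In the seven domains other than renal and hematological, one completed item sets the blank ones to not present, so the whole domain must be blank. A renal or hematological domain marked entirely as not applicable is coded as no. Only a domain still missing after these steps is affected.
- A reader might also infer that a lost Visit 2 laboratory sample cannot be recovered. SAP 6.4 arguably already admits the Visit 1 result: hematology, chemistry, urinalysis and the urine protein ratio are all drawn at Visit 1. The post-baseline wording in Appendix 1 may be meant only for later visits. This is an unreconciled ambiguity, not proof that recovery is barred.
- BILAG appears first at Visit 2 in the visible schedule, but part of the screening table is redacted. SAP 6.15 also refers to a separate derivation document that is not available here.
- The power table uses the rates and arm size of an endpoint that does not use BILAG. BICLA is analyzed only in participants with at least one A or two Bs at baseline, so 70 per arm need not apply. The table also charges every affected participant to the defect, although the remedy recovers only those scored C, D or E at the visit.
- Scoring unresolved composites as nonresponse is the plan's stated convention. Tablet capture and the eligibility committee's data-quality role make wholly blank domains unlikely.

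None of this removes the core point. NRI is meant for outcomes that cannot be determined, and here the outcome can be. Nor does any of it explain why the reduction part carries an exception that can never take effect.

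**Conclusion.** The rule is wrong as written, and the consequence is probably small. If a BILAG domain remains missing at baseline, both no-worsening rules become missing even where the visit score rules out a new A or B. BICLA is then a nonresponse at every post-baseline visit. SRI-4 is too, except under the participant-level reading in one uncommon pattern. The reduction part's exception has no effect on BICLA response.

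The missingness arises before the first dose, so the expected effect is attenuation in all arms. A reader might infer a bias toward one arm, or a threat to the primary result; neither follows. SLEDAI-4 and LLDAS do not use BILAG.

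The logic rests only on the SAP text. The size rests on an undocumented missingness rate and on borrowed SLEDAI-4 figures. At an assumed 1% to 2% the difference shrinks by 0.2 to 0.5 points and power stays above 80%; at 5% power is 77.6%. These figures are not estimates for SRI-4 or BICLA.

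**What to change.** Add one sentence to both no-worsening rules in SAP Appendix 1 (the stand-alone row and the second part of *BILAG improvement*): a domain missing at baseline and scored C, D or E at the visit counts as no new A or B, and the other domains decide. A domain missing at baseline and scored A or B at the visit stays unresolved, so no real worsening can be hidden. The same sentence should make clear that each exception applies to the domain concerned, which also closes the participant-level reading.

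Separately, reconcile the renal and hematological wording in Appendix 1 with the baseline definition in SAP 6.4. State whether a Visit 1 laboratory value may serve as the BILAG baseline and within what window. The window needs a decision because Visit 1 may fall 35 days before randomization and the BILAG carry-forward limit is 34 days.

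The cost is a few sentences before unblinding. No new data are needed, and the rule is applied without reference to treatment arm. Reporting the number of participants with an unresolved baseline domain, by arm, would show whether the point mattered.
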